4.2 Exclusion Criteria

Patients meeting **any** of the following criteria will be excluded from participation in the study:

- 1. Prior treatment with an anti-PD1 or anti-PD-L1 antibody
- 2. Eligible, to participate in a clinical trial of an alternative anticancer therapy targeting their disease which is open to accrual in France.
- 3. Concurrent steroid medication at a dose greater than prednisone 10 mg/day or equivalent (Appendix 7). For patients with germ-cell cancer, PCNSL concurrent steroid medication at a dose greater than prednisone 20 mg/day or equivalent.
- 4. Has active autoimmune disease that has required systemic treatment in the past 2 years (i.e. with use of disease modifying agents, corticosteroids or immunosuppressive drugs).

- Replacement therapy (eg., thyroxine, insulin, or physiologic corticosteroid replacement therapy for adrenal or pituitary insufficiency, etc.) is not considered a form of systemic treatment.
- 5. History of (non-infectious) pneumonitis that required steroids, or current pneumonitis.
- 6. History of severe hypersensitivity reaction to any monoclonal antibody therapy
- 7. Radiotherapy (except for brain and extremities) within 21 days prior to the first administration of IP.
- 8. Treatment with other investigational drugs or participation in another clinical trial within 21 days prior to the first administration of IP or concomitantly with the trial.
- 9. Has known symptomatic central nervous system (CNS) metastases. Patients with previously treated brain metastases may participate provided they are stable (without evidence of progression by imaging for at least four weeks prior to the first dose of trial treatment and any neurologic symptoms have returned to baseline), have no evidence of new or enlarging brain metastases, and are not using steroids for at least 7 days prior to trial treatment.
- 10. Has known carcinomatous meningitis or a history of leptomeningeal disease, except for patients with primary CNS lymphoma.
- 11. Serum creatinine > 1.5 xULN or glomerular filtration rate (GFR) < 50 ml/min.
- 12. Other malignancies within the past 5 years other than basal cell skin cancer or *in situ* carcinoma of the cervix.
- 13. Active serious infections in particular if requiring systemic antibiotic or antimicrobial therapy.
- 14. Active or chronic hepatitis B, hepatitis C and/or human immunodeficiency virus (HIV) infection (HIV 1/2 antibodies), or a known history of active *Tuberculosis bacillus*.
- 15. Has received a live vaccine within 30 days of planned start of study treatment.
- 16. **Note:** Seasonal influenza vaccines for injection are generally inactivated vaccines and are allowedActive alcohol or drug abuse.
- 17. Psychological, familial, sociological or geographical factors potentially hampering compliance with the study protocol and follow-up schedule.
- 18. Any condition which in the Investigator's opinion makes it undesirable for the subject to participate in the trial or which would jeopardize compliance with the protocol.

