3 TRIAL DESIGN

3.1 Evaluation Criteria

3.1.1 Primary Endpoint

Objective response rate per cohort, defined as the percentage of patients in each cohort with a complete response (CR) or partial response (PR) measured at the first scheduled disease assessment following study treatment initiation (Day 84, ± 7 days) as assessed by an Independent Review Committee (IRC) according to (i) the Response Evaluation Criteria in Solid Tumours version 1.1. (RECIST v1.1; Eisenhauer, 2009; Appendix 1) for patients with solid tumours, (ii) RECIST v1.1 combined with biomarker assessment (Fizazi, 2014; Appendix 2) for patients with germ-cell cancer, (iii) the International PCNSL cooperative group (IPCG) response criteria (Abrey, 2005; Appendix 3), (iv) the 'Lugano' criteria for response assessment using the fluorodeoxyglucose-positron emission tomography-computed tomography (FDG-PET-CT) five-point scale (5-PS; Barrington, 2014; Cheson, 2014; Appendix 4) and assessment of *Epstein-Barr* virus (EBV) load.

Patients who withdraw from the study prior to this time point and patients with non-evaluable disease will be considered as 'non-responders'in the analysis.

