 - Trophoblastic germ-cell tumour progressing after standard therapy.
 - Natural killer T-cell lymphoma: extranodal NK/T-cell lymphoma regardless of localization that is resistant or refractory to prior L-asparaginase therapy.
- 3. Metastatic disease or unresectable locally advanced malignancy that is resistant or refractory to standard therapy or for which standard therapy does not exist or is not considered appropriate by the Investigator.
- 4. Aged ≥ 18 years old for cohort 2 to 7 and aged ≥ 15 years old for patients included in cohort 1 (rare sarcoma).
- 5. Measurable disease defined:
 - according to RECIST v1.1 guidelines (Eisenhauer, 2009) for patients with solid tumours;
 - according to IPCG response criteria (Abrey, 2005) for patients with PCNSL;
 - according to RECIST v1.1 and / or abnormal levels of AFP, hCG and LDH for patients with germ-cell cancer;

- as focal uptake in at least one nodal or extra-nodal site with a Lugano 5-PS score of 4 or 5 (Cheson, 2014) for patients with NK/T-cell lymphoma,
- 6. Able to provide a FFPE biopsy sample of a metastatic site or primitive tumour tissue.

Note: Patients for whom suitable archived biopsy material is not available must be willing to undergo a biopsy of a tumour lesion prior to study entry, unless this is medically contraindicated (e.g. site inaccessible or patient safety concerns).

- 7. Patients must have a mandatory treatment-free interval of at least 21 days following previous systemic anti-cancer treatments.
- 8. Patients who have received previous systemic anticancer treatment and/or radiotherapy should have recovered from any treatment related toxicity, to a level of ≤ grade 1 (according to NCI-CTCAE criteria, v 4.0, Appendix 5) with the exception of Grade 2 alopecia.
- 9. Adequate hematologic function (absolute neutrophil count [ANC] \geq 1.0 x10⁹/L, platelets \geq 100 x10⁹/L, haemoglobin \geq 9 g/dL) measured within 14 days of treatment initiation unless due to lymphoma associated haemophagocytic lymphohistiocytosis (HLH).
- 10. Adequate renal function (creatinine clearance ≥ 50 mL/min using the MDRD or CKD EPI method) measured within 14 days of treatment initiation.
- 11. Adequate hepatic function (serum bilirubin ≤ 1.5 x the reference upper limit of normal (ULN) unless due to Gilbert's syndrome; ASAT and ALAT ≤ 3 xULN) measured within 14 days of treatment initiation unless due to lymphoma associated HLH. For patients with documented liver metastasis ASAT/ALAT ≤ 5x ULN is acceptable.

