5.9.2 Prohibited Concomitant Treatments

Subjects are prohibited from receiving the following therapies during the Screening and Treatment Phase (including retreatment for post-complete response relapse) of this trial:

- Antineoplastic systemic chemotherapy or biological therapy
- Immunotherapy not specified in this protocol
- Chemotherapy not specified in this protocol
- Investigational agents other than pembrolizumab
- Radiation therapy
 - Palliative radiation therapy to a single symptomatic lesion or to the brain may be allowed, provided the lesion is not a target lesion for RECIST v1.1 evaluation and the need for therapy does not equate to progressive disease. Patients with PD must discontinue study treatment.
- Live vaccines within 30 days prior to the first dose of IP and while participating in the trial. Examples of live vaccines include, but are not limited to, the following: measles, mumps, rubella, varicella/zoster, yellow fever, rabies, Bacillus Calmette–Guérin (BCG), and typhoid vaccine
- Systemic glucocorticoids at a dose greater than prednisone 10 mg/day or equivalent (Appendix 4). The use of physiologic doses of corticosteroids may be approved after consultation with the Sponsor.
- Other medications described in the exclusion criteria (Section 4.2)

Subjects who, in the assessment by the investigator, require the use of any of the aforementioned treatments for clinical management should be removed from the trial. Subjects may receive other medications that the investigator deems to be medically necessary.

There are no prohibited therapies during the LTFU Phase.

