7.1 Screening

Note: Patient inclusion is subject to a mandatory centralised pre-selection process in order to confirm specific eligibility criteria (see Section 3.4). Patient screening procedures may only be initiated after approval of this pre-selection request.

Written informed consent is to be obtained before any study related procedures are performed. If a protocol required screening procedure or assessment has been performed as part of the routine standard of patient care however, and has been performed within the study timeframe, the procedure or assessment does not need to be repeated, unless clinically indicated.

The following should be performed within **28 days** prior to the first administration of study treatment:

- Patient's written informed consent obtained
- Collection of demographic data: date of birth, gender, height and body weight
- Collection of cancer history (including verification of pathological diagnosis, date of diagnosis, stage at diagnosis, dates and sites of recurrent disease) and prior therapy (including name of agents, date of initiation, setting, date of last dose)
- Collection of other relevant medical history, and concomitant therapies
- Complete clinical examination (major body systems)
- Measurement of vital signs (blood pressure, seated heart rate, body temperature)
- Assessment of ECOG performance status
- Assessment of ongoing toxicities including pre-existing symptoms such as intestinal transit issues, dyspnoea and coughing, rash, nausea, headaches, signs of motor or sensory neuropathy and arthralgia. History of fever or recent infection must be investigated appropriately.
- Disease evaluation, including:

For patients with solid tumours:

- Clinical assessment of palpable or visual lesions.
- o Mandatory CT scan or MRI for baseline disease assessment.
- Other appropriate radiological assessment (e.g. FDG-labelled PET, PET-CT, metaiodobenzylguanidine [mIBG] scintigraphy, bone scan, ultrasonography), to be performed at the Investigator's discretion.
- o Appropriate biological assessments to be performed at the Investigator's discretion.
- Documentation of baseline tumour status including identification of all measurable and non-measurable lesions as per RECIST v1.1.

For patients with PCNSL, disease assessment should include:

- Gadolinium-enhanced MRI of the brain (may be substituted with contrast-enhanced CT scans in patients for whom MRI is medically contraindicated).

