Tumour lesions situated in a previously irradiated area, or in an area subjected to other loco-regional therapy, are usually not considered measurable unless there has been demonstrated progression in the lesion. Trial protocols should detail the conditions under which such lesions would be considered measurable.

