 total protein may have prognostic importance, the value of CSF total protein after therapy is unknown.
- At the time a CR is determined, the patient should have discontinued use of all corticosteroids for at least 2 weeks. Rare exceptions may be made for those patients receiving corticosteroids for another diagnosis (eg, panhypopituitarism).

Unconfirmed complete response (CRu) includes those patients who fulfill the criteria for CR with the following features/limitations:

- Any patient who fulfills all criteria for CR but continues to require corticosteroid therapy at any dose should be considered an unconfirmed CR. This is critical because corticosteroids may be oncolytic in treating occult tumor. In addition, corticosteroids may decrease gadolinium enhancement on MRI.
- Some patients will have a small but persistent enhancing abnormality on MRI related to biopsy or focal hemorrhage. It is often difficult to ascertain whether this represents a residual nidus of tumor or scar tissue. Adjunctive radiologic studies such as single-photon emission computed tomography or positron emission tomography may be helpful, but often the nature of these abnormalities may only be determined by observing the patient with serial scans. If the type of abnormality does not change

or slowly involutes over time without therapy and corticosteroids, it is reasonable to categorize it as a CR.

 Patients with a persistent minor abnormality on follow-up ophthalmologic examination (persistent nonmalignant cells in the vitreous, alteration of the retina/optic nerve that is not consistent with tumor infiltration) may be considered a CRu if this abnormality is unlikely to represent ocular lymphoma.

Partial response (PR) requires all of the following:

- A ≥ 50% decrease in the contrast-enhancing lesion seen on MRI as compared with baseline imaging.
- Corticosteroid dose is irrelevant to the determination of PR.
- Ophthalmologic examination should show a decrease in the vitreous cell count or retinal/optic nerve
 cellular infiltrate but may continue to show persistent malignant or suspicious cells. Color photos of
 the posterior pole of the eye should be obtained to document improvement in retinal/optic nerve
 infiltrates.

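### Exclusion 7 exempts brain radiotherapy from the 21-day washout in every cohort, so in primary CNS lymphoma radiotherapy shrinkage of the scored lesion can count as a Day-84 response to pembrolizumab

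*Protocol*

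**What the plan says.** **Eligibility.** Exclusion 7 (section 4.2, repeated in the synopsis) excludes "Radiotherapy (except for brain and extremities) within 21 days prior to the first administration of IP". It distinguishes neither cohorts nor lesions used for response from other lesions. The only other washout, inclusion 7 in section 4.1, is limited to systemic treatment: "Patients must have a mandatory treatment-free interval of at least 21 days following previous systemic anti-cancer treatments". Inclusion 8 asks for recovery from radiotherapy toxicity. The four-week imaging stability rule in exclusion 9 is worded for brain metastases.

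**Baseline.** Section 7.1 introduces the disease evaluation with "The following should be performed within 28 days prior to the first administration of study treatment". It also lets an assessment done in routine care within that window stand without repetition unless clinically indicated. Nothing says the scan must follow the last anticancer treatment.

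**Response.** The primary endpoint (section 3.1.1) is CR or PR at the first scheduled assessment, Day 84 ± 7 days. For primary CNS lymphoma, Appendix 3 requires for a PR "A ≥ 50% decrease in the contrast-enhancing lesion seen on MRI as compared with baseline imaging", along with ocular, CSF and no-new-site conditions. It has no rule on irradiated lesions. For solid tumours, Appendix 1 says irradiated lesions usually do not count as measurable unless they have progressed, and adds "Trial protocols should detail the conditions under which such lesions would be considered measurable". The protocol gives no such conditions.

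**Radiotherapy during the study.** Section 5.9.2 prohibits radiotherapy in Screening and Treatment. Palliative radiotherapy to a single symptomatic lesion or to the brain may be allowed "provided the lesion is not a target lesion for RECIST v1.1 evaluation" and if the need for it does not amount to progression.

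**The concern.** The endpoint compares the Day-84 scan with a baseline scan, and the estimate is read as the effect of pembrolizumab. That reading needs nothing other than pembrolizumab to have acted on the measured lesion between the two scans, and no carry-over from treatment just before. For most cohorts a brain exemption leaves this intact, because the measured disease lies elsewhere. In cohort 3 the exempted site is the measured site.

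With no control arm, radiotherapy shrinkage cannot be separated from drug effect. It would raise the reported response rate, and it enters the futility rule, which compares the rate with 0.10.

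**Working it through.** **1. Does any provision close the gap for cohort 3?**

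| Provision | Why it does not fully close it |
|---|---|
| Inclusion 7 | Systemic treatment only |
| Inclusion 8 | Concerns toxicity, not timing or lesion effect |
| Exclusion 9 | Worded for brain metastases |
| 5.9.2, ban from Screening onward | Screening begins after consent (section 3.2), so earlier radiotherapy is outside it |
| 5.9.2, target-lesion proviso | Refers to RECIST; cohort 3 uses IPCG |
| Appendix 1, irradiated lesions | RECIST only |
| Appendix 3 | Silent |

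**2. The route.** A routine-care brain MRI is done 28 days before first dose. Brain radiotherapy follows before consent. The patient then consents, the MRI is kept as baseline, and pembrolizumab starts. Neither exclusion 7 nor the section 5.9.2 ban prevents this sequence. A second route is brain radiotherapy after consent under the palliative exception, if its conditions are judged to be met.

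**3. Effect of one such response at the first look.** The protocol states no figure to reproduce here. Inputs are n = 10, p0 = 0.10, 85% confidence (synopsis, section E) and a Jeffreys or uniform prior (section 10.3, not fixed). The posterior is Beta(a + y, b + 10 − y), with a = b = 0.5 or 1.

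| Prior | 0/10 responses | 1/10 responses | Futility decision at 0.85 |
|---|---|---|---|
| Jeffreys | Beta(0.5, 10.5): 0.858 | Beta(1.5, 9.5): 0.439 | Stop becomes continue |
| Uniform | Beta(1, 11): 1 − 0.9^11 = 0.686 | Beta(2, 10): 1 − 0.9^11 − 11 × 0.1 × 0.9^10 = 0.303 | Continue both times |

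Section 10.3 says the threshold usually lies between 0.8 and 0.9. Under Jeffreys the reversal also occurs at 0.80 but not at 0.90, since 0.858 is below 0.90. Under the uniform prior 0/10 does not stop at any of the three.

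**4. Effect on the estimate.** Each response due to radiotherapy alone adds 1/n: 10 percentage points at n = 10 and 2 points at n = 50.

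**5. Illustration over the whole cohort.** Let s be the share irradiated at the measured site close to entry, and r the chance that radiotherapy alone gives a Day-84 response. Both are assumptions; the protocol gives neither. With drug response rate p,

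observed rate = (1 − s)p + s[1 − (1 − p)(1 − r)].

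For p = 0.05, s = 0.10, r = 0.3: 0.9 × 0.05 + 0.1 × (1 − 0.95 × 0.7) = 0.0785. The chance of passing every futility look at n = 10, 15, ..., 50 (threshold 0.85, exact binomial recursion, futility rule only) is:

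| s | r | Observed rate (p = 5%) | Pass, uniform | Pass, Jeffreys |
|---|---|---|---|---|
| 0 | – | 5.0% | 0.33 | 0.20 |
| 10% | 0.3 | 7.9% | 0.62 | 0.42 |
| 10% | 0.8 | 12.6% | 0.88 | 0.69 |
| 20% | 0.3 | 10.7% | 0.81 | 0.60 |
| 20% | 0.8 | 20.2% | 0.99 | 0.89 |

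Under the uniform prior the first look is unaffected, but passage through the later looks is.

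**6. Systemic treatment.** The imaging window minus the washout is 28 − 21 = 7 days, so a baseline scan could precede the last prior systemic dose by up to 7 days. Section 5.9.2 bars systemic antineoplastic treatment in Screening, so this arises only when a pre-consent scan is reused.

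**The case against.** The strongest reply is that section 5.9.2 already prohibits radiotherapy from Screening onward. Its exception is discretionary and palliative, and it requires that the need for radiotherapy is not progression, a condition not tied to RECIST that applies to cohort 3. Central pre-selection sees prior treatments and disease status, and an investigator may repeat the MRI. All of this stands, and it makes the event less likely. A reader might infer that brain radiotherapy could be given freely on any day between baseline and first dose. The documents do not support that: it must fall before consent or within the palliative exception. Those two routes remain, because pre-selection has no stated radiotherapy criterion and a repeat scan is needed only if clinically indicated.

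A reader might extend the point to limb sarcoma with equal force. Appendix 1 usually denies measurability to irradiated lesions that have not progressed, inclusion 5 requires RECIST-measurable disease, and section 5.9.2 protects target lesions from Screening onward. What remains is smaller: the word usually, the missing conditions that Appendix 1 asks for, and radiotherapy completed before consent.

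A reader might also conclude that exclusion 9 leaves the exemption with no use outside cohort 3. It does not. Exclusion 9 requires stability on imaging and does not bar recent radiotherapy to stable brain metastases, and palliative limb fields arise in every cohort.

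Finally, one radiotherapy response does not by itself reopen enrolment early. Section 10.2 also requires collegiate confirmation, a recognised clinical need and a Steering Committee decision.

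**Conclusion.** The concern holds for cohort 3. Exclusion 7 exempts the site that carries the endpoint, and the provisions that might compensate are limited to systemic treatment, brain metastases, RECIST targets or the period after consent. Limb sarcoma and the 7-day systemic gap are lesser points with the limits given above.

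The direction of bias is upward. Its size is unknown from the protocol, because neither the share irradiated nor the radiotherapy response rate is given; the table in the working is illustrative. What needs no such assumption is the weight of one misattributed response at n = 10: it reverses a futility stop under Jeffreys at 0.85, narrowly, and changes no futility decision under the uniform prior. It would go too far to say that the cohort 3 result is materially inflated, or that the interim decision was affected.

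**What to change.** 1. Reconcile exclusion 7, section 5.9.2 and Appendices 1 and 3 on whether a recently irradiated lesion may be the lesion assessed at Day 84, and state the conditions Appendix 1 asks for. What the radiotherapy rules should be is a clinical matter for the sponsor; no washout length or palliative radiotherapy rule is proposed here.
2. In section 7.1, require the baseline disease evaluation used for response to be performed after the end of the last anticancer treatment, radiotherapy or systemic, including when a routine-care scan is reused.
3. Prespecify that the Day-84 response rate, at the interim looks and the final analysis, is also reported with patients counted as non-responders if they were irradiated at the assessed site within 21 days before first dose, or between baseline and Day 84. The SAP was not available; if it already contains this, a cross-reference is enough.

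The cost is an amendment to wording, some baseline scans timed later or repeated, and possibly a slightly lower response rate. The third step remains possible after cohort 3 has finished enrolling, provided radiotherapy dates and sites are on record.

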5 TRIAL TREATMENTS

5.1 Trial Products and Treatments

The investigational product **pembrolizumab** (MK-3475) is an IV administered human monoclonal antibody manufactured by Merck Sharp & Dohme Corp that blocks the interaction between the PD-1 receptor and its ligands, PD-L1 and PD-L2.

Pembrolizumab solution for infusion is supplied as 4 ml vials of solution for injection (100mg / 4ml). Pembrolizumab Solution for Infusion is a liquid DP (manufactured using the fully formulated IP with L-histidine as a buffering agent, polysorbate 80 as a surfactant, and sucrose as a stabilizer/tonicity modifier).

5.2 Therapeutic Scheme

Pembrolizumab will be administered by intravenous infusion over 30 minutes at a dose of 200 mg in adult patients, or at a dose of 2mg/kg (maximum dose 200 mg) for patients 15-17 years old, on Day 1 of every 21-day cycle. Every effort should be made to target infusion timing to be as close to 30 minutes as possible; given the variability of infusion pumps from site to site however, a window of -5 minutes and +10 minutes is permitted (i.e., infusion time is 30 minutes: -5 min/+10 min).

The Pharmacy Manual contains specific instructions for the preparation of the pembrolizumab infusion fluid and administration of infusion solution.

Treatment should be continued as long as clinical benefit is observed or until treatment is no longer tolerated by the patient (Section 3.6) up to a maximum of 24 months (or 35 cycles, whichever is longer).

